7.3 Implementation Process and Outcome Measures

7.3.1 Identifying Facilitators and Barriers to Implementation Success

Both quantitative and qualitative measures will be collected on factors hypothesized to be related to implementation success. Measures of implementation process capturing elements organized by the domains in the Consolidated Framework for Implementation Research (CFIR; (Damschroder and Hagedorn, 2011)) were used to guide measurement selection. This framework identifies the domains of intervention characteristics (e.g., complexity, relative advantage), inner setting (e.g., readiness, clinical leadership), individual characteristics (e.g., provider beliefs, self-efficacy), and implementation process (e.g., fidelity and feasibility) as necessary to understand the factors contributing to and barriers preventing implementation success. Table 4 summarizes these domains and the associated measures applicable to this trial.

7.3.2 Table 4: Implementation Measures Organized by the Consolidated Framework for Implementation Research Constructs

Construct	Measure	Data Sources (Timeline)
Intervention Characteristics	Intervention Source Evidence Strength & Quality Relative Advantage Adaptability Complexity Design Quality and Packaging Cost	ORCA (Before and after each wedge intervention) Staff Structured Interviews (After each wedge intervention and study conclusion) Coaching Session Progress Notes Internal Implementation Team Meeting Notes NMS Assessments and Staff Structured Interviews
Outer Setting	Patient Needs & Resources Peer Pressure External Policy & Incentives	Site Mapping Needs Assessment and Progress Notes (Pre-implementation phase before each wedge intervention) Coaching Session Progress Notes Staff Structured Interviews (After each wedge

Construct	Measure	Data Sources (Timeline)
		intervention and study conclusion)
Inner Setting	Structural Characteristics Culture Implementation Climate (Tension for Change, Compatibility, Relative Priority) Learning Climate Readiness for Implementation (Leadership Engagement, Available Resources)	Site Mapping Needs Assessment and Progress Notes (Pre-implementation phase before each wedge intervention) Coaching Session Progress Notes Internal Implementation Team Meeting Notes ORCA (Before and after each wedge intervention) Readiness/preparedness rulers (Before and after each wedge intervention) Staff Structured Interviews (After each wedge intervention and study conclusion)
Individuals	Knowledge and Beliefs about the Intervention Self-efficacy Individual Stage of Change Individual Identification with Organization Other Personal Attributes	ORCA (Before and after each wedge intervention) Readiness/preparedness rulers (Before and after each wedge intervention) Staff Structured Interviews (After each wedge intervention and study conclusion)
Process	Planning Engaging Executing Reflecting & Evaluating	Critical Action Checklists (Throughout trial, weekly) Implementation Process Fidelity Checklist (Throughout trial, monthly) Daily Medication Administration Log (Throughout trial, daily) Coaching Session Progress Notes (Throughout trial, weekly or more frequently based on site needs) Internal Implementation Team Meeting Notes (Throughout trial as needed) Staff Structured Interviews (After each wedge intervention and study conclusion) Patient End of Induction Survey (At end of detox admission) Patient Treatment Satisfaction Survey (At trial completion) Organization Level Clinical Implementation Data Form (Before and after each wedge intervention)

7.3.3 Implementation Related Outcome Measures

In addition to the above measures considering factors impacting successful implementation, implementation-related outcome measures will also be collected. These will be organized according to the RE-AIM framework, designed to enhance the public health impact of research evidence through coherent organization of outcomes related to implementation (Glasgow *et al.*, 1999).

This framework includes the domains of: **Reach** to the intended target population, **Effectiveness**, **Adoption** by target staff and institutions, **Implementation** consistency (including fidelity to the Intervention), and **Maintenance** of the intervention over time by the target providers. The following

table describes study related measures organized according to this framework:

7.3.4 Table 5: Implementation Outcome Domain

Implementation Outcome Domain	Specific Study Measures
Reach	Clinic level data on percent of individuals with OUD screened for trial participation, percentage of individuals with OUD who receive XR-NTX during inpatient detox or residential rehab.
Effectiveness	Secondary clinical outcomes related to effectiveness will be gathered as described above (Table 3).
Adoption	An implementation checklist will capture all planned implementation processes, including the number of providers participating in each implementation activity.
Implementation	Fidelity to suggested clinical guidelines for trial participants will be gathered for each patient throughout the detoxification and rehabilitation stay via a critical action checklist.
Maintenance	Qualitative data (structured progress notes and staff interviews with key personnel) will capture barriers and facilitators that inform modifications and adaptations to implementation strategies to support long term adoption of the study procedures.

7.3.5 Integration Process for Iterative Improvement of Implementation Facilitation

All implementation measures will be analyzed by categorizing individual facilitators and barriers within the framework of the CFIR model. These measures will be assessed after each stepped wedge across various qualitative data including structured notes from Site Mapping meetings and coaching sessions, internal implementation team meeting notes, and staff structured interviews at the end of each stepped wedge.

Structured progress notes will contain sections for identified barriers and facilitators captured through site meetings and internal implementation team discussions. In addition, any modifications or adaptations made throughout the step wedge will be documented using these structured progress notes. Structured interviews with clinical staff and participants will be digitally

recorded, transcribed, and coded based on the CFIR framework using Atlas.ti software (i.e., intervention characteristics, patient/provider characteristics, internal setting factors, and external setting factors). Qualitative data analysis will involve conceptual mapping of identified barriers and facilitators across the CFIR framework), and will inform modifications and adaptations to implementation strategies and the IF package. Modifications and adaptations to implementation strategies will be categorized using the FRAME-IS model, the ERIC taxonomy for naming of implementation strategies, and Proctor *et al.*'s guidance on specifying implementation strategies. This systematic approach will be used to make improvements on implementation procedures and contribute to an improved implementation package at the trial conclusion

8.0 STUDY POPULATION

Study participants are treatment-seeking heroin- and/or prescription opioid-dependent volunteers, without chronic pain requiring opioid therapy, who are willing to undergo opioid withdrawal and accept relapse prevention treatment with XR-NTX. The target recruitment is approximately 75 participants per site or approximately 450 participants in total across 6 sites, with approximately 225 participants treated using SP and approximately 225 participants treated using the RP.

8.1 Participant Inclusion Criteria

Study participants must meet all of the following inclusion criteria in order to be eligible to participate in the study:

1. 18 years of age or older.
2. Meets current DSM-5 criteria for opioid use disorder.
3. Seeking treatment for opioid use disorder, willing to accept treatment with XR-NTX and, in the judgment of the treating physician, is a good candidate for naltrexone- based treatment.
4. Willing and able to provide written informed consent.
5. Able to speak English sufficiently to understand the study procedures and provide written informed consent to participate in the study.
6. If female of childbearing potential, willing to practice an effective method of birth control for the duration of participation in the study.

8.2 Participant Exclusion Criteria

All individuals meeting any of the following exclusion criteria will be excluded from study participation:

1. Serious medical, psychiatric or substance use disorder that, in the opinion of the study physician, would make a detoxification and naltrexone initiation, or maintenance treatment with XR-NTX, hazardous (relative contra-indications) or requires a different level of care. Examples include:
 - a) Disabling or terminal medical illness (e.g., uncompensated heart failure, severe acute hepatitis, cirrhosis or end-stage liver disease) as assessed by medical history and/or review of systems.
 - b) Severe, untreated or inadequately treated mental disorder (e.g., active psychosis, uncontrolled manic-depressive illness) as assessed by history and/or clinical interview.
 - c) Current severe alcohol, benzodiazepine, or other depressant or sedative hypnotic use likely to require a complicated medical detoxification (routine alcohol and sedative detoxifications may be included).
 - d) Suicidal or homicidal ideation that requires immediate attention.

2. Known allergy or sensitivity to buprenorphine, naloxone, naltrexone, polylactide-co-glycolide, carboxymethylcellulose, or other components of the Vivitrol® diluent.
3. Maintenance treatment with methadone within 14 days of consent.
4. Maintenance treatment with buprenorphine unless the patient is determined to have a poor treatment response (in the form of buprenorphine non-adherence with or without the use of illicit opioids), warranting change to XR-NTX treatment.
5. Presence of pain of sufficient severity as to require ongoing pain management with opioids.
6. Circumstances (legal, personal, occupational) that would threaten the feasibility of XR-NTX treatment or make another treatment (e.g., buprenorphine or methadone) a better choice.
7. Are currently in jail, prison or other overnight facility as required by court of law or have pending legal action that could prevent participation in study activities.
8. If female, currently pregnant or breastfeeding, or planning on conception.
9. Body habitus that, in the judgment of the study physician, precludes safe intramuscular injection of XR-NTX (e.g., BMI>40, excess fat tissue over the buttocks, emaciation).
10. Admitted to the inpatient detoxification or residential rehabilitation unit more than 4 calendar days prior to enrollment into to SP or RP.

8.3 Special Populations to Consider

This study is likely to enroll persons involved in the criminal justice system, many of whom are expected to be in treatment at the clinical sites participating in this study. The study will exclude persons incarcerated/detained in a correctional facility, but will not exclude parolees, probationers, or persons in sentencing diversion or drug court programs who are enrolled at participating sites. Some of these subjects may be classified as prisoners per 45 CFR 46 Subpart C.

8.4 Strategies for Recruitment and Retention

Recruitment efforts will vary per site and may broadly include site staff education and distribution of study materials, community or participant-level outreach and advertisements, and the encouragement of word-of-mouth referrals among site patient populations. During (or prior to) the first four calendar days of an inpatient admission, clinical and/or research staff will evaluate all admitted patients for XR-NTX and provide information about the study to all patient-participants that express interest in treatment with XR-NTX.

9.0 SITE SELECTION

9.1 Number of Sites

The study is conducted at six sites that will be recruited from the NIDA National Drug Abuse Treatment Clinical Trials Network (CTN). Each of the sites will be expected to enroll approximately 1-2 eligible participant(s) per week over the 70 weeks recruitment period for the total N=450 enrolled.

9.2 Site Eligibility

To be included in the study, the selected sites must have the following characteristics:

1. Provide opioid detoxification services (inpatient/residential) where participants can be maintained opioid-free.
2. Able to provide treatment in hospital or residential treatment for at least the 14 days needed to carry out the SP initiation regimen.
3. Have the capacity to provide ongoing treatment with XR-NTX on an outpatient basis for at least 2 months after the induction and administer subsequent XR-NTX injections.
4. Have the capacity to provide outpatient care including medical management and counselling (at least one group and/or individual counseling session per week).
5. Have the capacity to provide psychiatric evaluation and either offer treatment for co-occurring psychiatric disorders or provide linkage to psychiatric care.
6. Currently offering XR-NTX induction using buprenorphine taper and a wait period for individuals entering treatment with active substance use and requesting XR-NTX.
7. Have no experience initiating patients onto XR-NTX using a RP.
8. Agree to implement the suggested RP as the induction method for patients attempting to transition from active opioid use to XR-NTX using the implementation regimen included in the study.
9. Have an adequate flow of patients entering treatment as to provide a sufficient population of potential participants to achieve study enrollment goals. We predict that with 3-5 patients admitted each week for “detoxification,” at least 1 participant per week should be interested in XR-NTX induction and be eligible to enroll into the study (other will initiate agonist maintenance).
10. Have leadership desiring to adopt XR-NTX initiation (SP and RP) as routine clinical practice for patients requesting detoxification.
11. Have the ability to provide deidentified information on individuals who were admitted to the unit during the study period but were not enrolled in the study.
12. Can provide space and resources for up to 6 study-supported staff.
13. With support from the study budget, able to enroll participants who do not have resources or insurance coverage to pay directly or through a third party for treatment.

9.3 Rationale for Site Selection

The volume of patients admitted to the unit must be adequate to ensure a steady stream of eligible patients for recruitment. A diverse, representative sample of patients and unit characteristics is desirable to enhance the external validity of the study. Geographical diversity of settings is desirable and research experience and successful participation in prior studies is essential as it provides evidence of the feasibility of study implementation.

Clinical experience using the standard method of XR-NTX induction with buprenorphine taper followed by a waiting period before XR-NTX induction is the standard of care in many treatment programs. Including only programs with experience with this method will allow for an appropriate comparison between the RP and SP methods of induction without the need for significant implementation or training to provide the SP. At the same time, we will not include sites experienced with the RP. Reduction of site variance in this research study will improve the power in statistical analysis to detect an effect for the primary outcome.

The research staff will preferably have experience working in the addiction treatment setting and therefore can be quickly integrated into the team.

10.0 STUDY PROCEDURES

Schematic of study phases is presented in Figure 1.

10.1 Pre-screening, Consent and Screening (Phase 1)

Participants will be recruited from the population of individuals presenting for treatment of opioid use disorder at the participating study sites.

Pre-screening will be completed before participants are approached for informed consent. All patients admitted to the unit with an OUD diagnosis should be pre-screened for the study and entered on the Participant Pre-Screening Log as well as on the pre-screening enrollment form in Advantage eClinical. The following will be assessed at pre-screening: current and active OUD, demographics, eligibility to receive XR-NTX and willingness to participate in the study.

All participants who are interested may begin the informed consent procedures up to 7 calendar days prior to the inpatient admission or during the first four calendar days of admission. All participants must sign the informed consent and complete screening procedures prior to the fourth calendar day of admission to be eligible to enroll in the Rapid Procedure or Standard Procedure. The timing of consent and screening procedures is flexible, and allows sites to customize recruitment, consent, and screening procedures to accommodate local conditions. Obtaining consent and screening/baseline data early in the admission will allow a full accounting of persons interested in study enrollment. For individuals consenting after admission, data will be collected about medication administration starting from admission using medication flowsheets and EMR abstraction (performed and confirmed by study staff).

10.1.1 Informed Consent Procedures for Participants

Candidates for the study are given a current IRB-approved copy of the Informed Consent Form to read. Appropriately qualified and trained study personnel explain all aspects of the study in lay language and answer all the study candidate's questions. Study procedures and the potential risks and benefits of participating in the trial will be explained. Staff will be available to answer questions about the consent form while participants are reviewing it.

Prior to signing the consent form, the participant must pass a brief consent quiz to illustrate comprehension of the study activities - understanding of the project, the purpose and procedures involved, and the voluntary nature of his/her participation. Those who cannot successfully answer quiz items have the study re-explained by research staff with a focus on aspects they did not understand. Those who demonstrate understanding of the study and voluntarily agree to participate are asked to sign the Informed Consent Form. After passing the quiz and signing the consent form, participants will be offered a copy of the forms to keep for their records. The informed consent process and quiz will take approximately 30-45 and 5 minutes to complete, respectively.

Given the multi-site nature of the trial, it is possible that ancillary studies, or long term follow up studies, will be proposed before or after the study begins recruitment. For this reason, during the informed consent process, we also will seek permission to contact the participant in the future

about other study opportunities.

Participants are not administered any study assessments or procedures prior to signing informed consent. The informed consent includes a HIPAA Authorization to permit study staff to access the participant's medical records at the study site relating to the inpatient admission; the purpose of this is to capture study related clinical information that is collected during routine treatment (daily vitals, daily COWS, medication administration log, etc.).

10.1.2 HIPAA Authorization and Medical Record Release Forms

Study sites may be required by their institutions to obtain authorization from participants for use of protected health information (PHI). Sites will be responsible for communicating with the IRB of Record or any local Privacy Boards and obtaining the appropriate approvals or waivers to be in regulatory compliance.

10.1.3 Screening/Baseline Visit

Screening and baseline assessments are detailed in Section 12 and capture participant demographics; medical, psychiatric, drug use, and treatment history; quality of life; and current health status. Urine testing will also be performed. Following obtainment of consent and the final confirmation of eligibility, participants are considered enrolled into SP or RP and begin completing baseline assessments.

10.2 Treatment Initiation

To maximize generalizability, this study is designed to permit consent of participants before and during the first four calendar days of inpatient treatment (Day 1 is day of admission). Patients judged clinically to be good candidates for detoxification and XR-NTX induction will, upon admission to the unit, begin treatment with non- opioid medications (mainly clonidine) and buprenorphine will be administered to address withdrawal symptoms as they emerge. Sites will agree to this regimen as their standard practice for the first four calendar days of inpatient-residential treatment. During the first four calendar days of admission, patients will have the opportunity to consent to the study, and concurrent treatment will follow the SP or RP, depending on which procedure the site is offering at that time per the study design.

10.3 Randomization

Randomization will be performed at the site level. Six sites that have the required characteristics to be included in this study will be randomized to the order in which they begin to implement the RP. Patient-participants will be treated with the SP or RP according to which procedure is being used at the site at the time the patient is admitted.

The randomization of each site will follow the stepped-wedge design (Table 1). At the selected time points as described in the Study Timeline section , one randomly selected site will make a "step" and will cross-over from the standard to the Rapid XR-NTX induction. Note that the first randomized site will be in the Rapid Procedure arm for the entire duration of the study whereas the 6th site (after 5 sites have been randomized to the Rapid Procedure) will be in the Standard Procedure arm for the entire duration of the study and will never switch to the Rapid Procedure.

The DSC statistician will conduct the randomization and inform the sites eight weeks before the selected site is scheduled to transition.

10.4 Inpatient Treatment/Intervention (Phase 2)

Participants are inducted onto their assigned XR-NTX induction regimen: Standard (Table 6A) or Rapid (Table 6B). These regimens are guidelines to be applied by the clinical teams with coaching from the lead team and may be modified by the site clinician based on the clinical status of each patient.

10.4.1 Standard Induction Procedure (SP)

SP includes stabilization on buprenorphine (6-8 mg) on Day 1 followed by a taper over the subsequent 4 days (Table 6A), however this schedule may be modified by the site clinician to suit the clinical status of each patient. Depending on the level of physical dependence, time from the last dose of an opioid, type of an opioid (prescription opioid, heroin, or fentanyl), and the severity of withdrawal, participants may be required to wait additional time and receive symptomatic treatment until it is safe for them to start taking buprenorphine.

After the completion of buprenorphine taper, participants will enter a washout period of at least 8 days. Adjunctive (non-opioid) medications will be administered during the washout period, as needed, to alleviate significant withdrawal symptoms, with choice of medications and doses as routinely used at the site. On the last day of the taper, participants will be evaluated for eligibility to receive XR-NTX injection, as it is routinely used at the site. This may include a naloxone challenge (e.g., 0.8-1.2 mg IM), a naltrexone titration (e.g., 25 mg PO), and/or a urine toxicology negative for buprenorphine and other opioids (as in CTN-0051). Once found eligible, an XR-NTX injection will be given.

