The research recruitment phase begins with informed consent up to one week before or up until the fourth day of inpatient admission to the study site. During the inpatient admission intake/evaluation or the first four days of an inpatient admission, clinical staff, as part of standard clinical procedures, will conduct a medical and psychiatric workup, and conduct a shared – decision-making process regarding choice of maintenance medication to be initiated during the inpatient stay. During this process research staff will provide information about the study to potential participants, describing XR-NTX as an option for relapse-prevention to opioid dependence following detoxification, and the study plan to monitor the progress of patients undergoing initiation and initial months of treatment with XR-NTX using materials prepared for the study. For scheduled admissions, this information may be provided in advance of the admission. Once a patient decides (with their clinicians) to pursue XR-NTX treatment, then the patient can be offered informed consent to participate in the study.

After the participant provides written informed consent, the participant will be evaluated for study eligibility. Eligible participants will continue with study assessments. Participants may be stabilized

on buprenorphine before study enrollment but those who received methadone at treatment outset (e.g., in the ER or upon arriving at the unit) are not eligible for enrollment.

Clinical Induction Procedures

Following the initial buprenorphine treatment, the units will provide participants with treatment guided by the regimen for the respective study arm as implemented by clinical staff at the detoxification program (Tables 6A and 6B).

Standard Procedures: The plan is for 13-14 days from first dose of buprenorphine in the Standard Procedures (SP) for induction, detailed in Table 6A; this includes a 5-day buprenorphine taper followed by an 8-day washout before being eligible for the XR-NTX injection (as determined by the naloxone challenge, naltrexone titration, or toxicology). In case that participant does not meet criteria of eligibility by Day 14, the eligibility determination can be repeated on subsequent days. Since the SP regimen will be the standard of care for XR-NTX initiation during the SP phase of the participation of a Site, there will be flexibility based on clinical judgment.

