10.4.2 Table 6A. Standard Induction Procedures

Day 1	Participants will receive buprenorphine 6 mg. If continue to experience significant withdrawal (COWS >6) they can receive additional 2-4 mg.
Day 2	Buprenorphine 6 mg in AM
Day 3	Buprenorphine 4 mg in AM
Day 4	Buprenorphine 2 mg in AM
Day 5	Buprenorphine 1 mg in AM
Days 6-13	Adjunctive medications as needed (i.e., clonidine and clonazepam)
Day 13 or 14	XR-NTX eligibility determination followed by the XR-NTX injection

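### Protocol 10.4.1 sets the SP eligibility evaluation on the last day of the buprenorphine taper, which contradicts its own washout of at least 8 days and the Day 13 or 14 timing in Table 6A

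*Protocol*

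**What the plan says.** Protocol 10.4.1 describes SP in prose. Buprenorphine starts on Day 1 and is tapered over the next four days, with a reference to Table 6A. Then: "After the completion of buprenorphine taper, participants will enter a washout period of at least 8 days". A sentence on adjunctive medication during the washout follows, and after it: "On the last day of the taper, participants will be evaluated for eligibility to receive XR-NTX injection". The evaluation follows the site's usual practice. It can consist of a naloxone challenge, a naltrexone dose, a urine test negative for buprenorphine and other opioids, or a combination of these. The paragraph closes: "Once found eligible, an XR-NTX injection will be given".

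Table 6A (Protocol 10.4.2) gives the day-by-day schedule. Its Day 5 row reads "Buprenorphine 1 mg in AM" and is the last buprenorphine row. Days 6 to 13 carry adjunctive medication only. The row for Day 13 or 14 reads "XR-NTX eligibility determination followed by the XR-NTX injection". SAP 2.2.3, Table 3, has the same rows.

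Three other places bear on the timing. Protocol 6.1.4.1 describes a five-day taper "followed by an 8-day washout before being eligible for the XR-NTX injection" and lets the determination be repeated if criteria are not met by Day 14. Protocol 2.4 puts the naloxone challenge and the injection 13 or 14 days from the first buprenorphine dose. Protocol 16.1.2 puts the end of SP induction at about Day 13.

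**The concern.** Section 10.4.1 is procedural text for the control arm. A reader who follows its evaluation sentence literally arrives at a different day from a reader who follows Table 6A, and nothing in the section says which one governs.

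The protocol itself treats this timing as relevant to safety. Section 4.1.1 explains the delay after the last agonist dose as a way to limit the risk of precipitated withdrawal, and Section 12.3.13 lists precipitated withdrawal within a targeted safety event. Two of the three listed eligibility tests involve an opioid antagonist.

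A literal reading might also go unnoticed. Section 17.15 does not count variations in clinical procedures as protocol deviations, and Section 6.2 gives SP sites a brief overview rather than systematic implementation support.

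**Working it through.** No sample-size or power formula is involved. The check is a day count, using Table 6A's numbering with the first buprenorphine dose on Day 1.

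**Inputs**
- Taper: Day 1 plus 4 further days (10.4.1), with the last dose on Day 5 (Table 6A).
- Washout: at least 8 days after the taper (10.4.1); Days 6 to 13 (Table 6A).
- Evaluation: last day of the taper (10.4.1); Day 13 or 14 (Table 6A and SAP Table 3).
- Injection: once the participant is found eligible, with no day stated (10.4.1); Day 13 or 14, after the determination (Table 6A).

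**Reproducing Table 6A's figure**
- Last taper day: 1 + 4 = Day 5.
- Eighth washout day: 5 + 8 = Day 13.
- First day after eight full washout days: 13 + 1 = Day 14.

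A five-day taper plus eight washout days therefore gives Day 13 or 14, as the table states. The table, Section 6.1.4.1 and the washout sentence in 10.4.1 are consistent with one another.

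**The evaluation sentence in 10.4.1**
- Evaluation day: Day 5.
- Washout days elapsed: 5 − 5 = 0, against a stated minimum of 8.
- Gap to Table 6A: 13 − 5 = 8 days, or 14 − 5 = 9 days.
- Buprenorphine on that day: yes, 1 mg in the Day 5 row.

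Section 2.4 counts days from the first dose rather than numbering them. Taken as elapsed days, that would give Day 1 + 13 = 14 or Day 1 + 14 = 15, which does not narrow the gap.

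There is also a tension inside 10.4.1. One listed test is a urine sample negative for buprenorphine, which fits poorly with a day on which Table 6A still gives the drug.

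**The case against.** The strongest reply is that this is a drafting slip. In 10.4.1 the evaluation sentence comes after the washout sentences, one of the tests looks for absence of buprenorphine, and the other timing statements in both documents put eligibility, injection or both after the washout. That is a reasonable inference, but the documents do not say it, and a slip in a procedural sentence would still need correcting.

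A second reply is that literal use is unlikely. Section 10.4 names Table 6A as the Standard regimen, and the table is clear. Section 9.2 requires sites that already induct with a taper and a wait and can provide at least 14 days of treatment. SP training rests mainly on the prescribing information (6.2), which Section 4.1.1 describes as a 7 to 10-day delay after the last agonist dose. The evaluation follows local routine and need not involve an antagonist. All of this stands and lowers the practical risk. It does not make the two timings compatible.

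A third reply is that Sections 10.4 and 10.4.1 let the site clinician modify the regimen. That flexibility covers an individual patient's clinical status. It does not reconcile two different default days.

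A reader might go further and infer that 10.4.1 orders the injection itself on the last taper day. It does not: only the evaluation is tied to that day, and the injection is conditional and undated. Table 6A links determination to injection, but in the same row that says Day 13 or 14, so it cannot be borrowed to put the injection on Day 5.

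**Conclusion.** The contradiction is real. It lies within 10.4.1, and between 10.4.1 and Table 6A, Protocol 2.4, 6.1.4.1 and 16.1.2, and SAP Table 3. Its size is 8 to 9 days in the default timing of the SP eligibility evaluation, assuming the taper follows Table 6A without individual modification. The consequence supported by the documents is a patient-safety ambiguity in the control-arm procedure: the literal text allows an optional antagonist test on a buprenorphine day. How many participants, if any, were evaluated that way cannot be derived.

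A reader might infer that the SP success rate, the time to injection or the power is distorted. The documents do not show this. The planned 450 participants and the power of 0.887 do not use this sentence, and the primary outcome in SAP 8.1 is receipt of the injection on the unit within 30 days of admission, whatever day eligibility is tested. An effect would require sites to have acted on the literal text, and nothing in either document indicates that they did.

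**What to change.** Reconcile Protocol 10.4.1 with Protocol 2.4, 6.1.4.1 and Table 6A and with SAP Table 3, so that one timing of the SP eligibility evaluation appears throughout. The sponsor's clinicians should decide which timing is right and whether 10.4.1 should also state when the injection follows.

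If any site is still enrolling in SP, send it a clarification. If not, a documented correction is enough. SAP version 2.0 is dated April 2023, and its Table 55 shell already carries 415 participants (190 Standard, 225 Rapid), which suggests that enrolment was far advanced or finished, though the SAP does not say so. The daily medication log summarised under SAP 6.0 can show which medications were actually given on each induction day.

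The cost is a clarification letter or a minor amendment. The design, the sample size and the primary analysis do not change.
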